At home, care-givers will record on a diarrhoea diary the frequency of stool each 24 hours, the stool consistency and time of cessation of diarrhoea. (Definitions below). After 7 days if diarrhoea continues, caregivers will be trained to prepare Diet B and will be instructed to feed Diet B - a milk free diet containing rice-cereal, vegetable oil, egg albumin and glucose mixture. The second diet (B) will also be fed for 7 days. For partially breastfed children the diets will be offered to attain energy intake >75 kcal/kg/day and for non-breastfed child the energy intake will be 110 kcal/kg/day. In addition multivitamin drops and zinc acetate are standard therapy for PD patients and will be given routinely to all children from the beginning of the study and for the following three weeks (Table 2). The dosage of multivitamin syrup will be 1 ml twice daily and Zinc acetate 10 mg twice daily. Oral rehydration with standard WHO-ORS will continue to maintain hydration to replace ongoing liquid stool losses until cessation of diarrhoea. The number of ORS packets used will be recorded.

On day 7 after beginning of diet A, if the patients are found to have normal stool (soft or formed), they will continue diet A.

After 7 days of second dietary regime, if diarrhoea persists, the patients will be admitted to the inpatient department for further evaluation and management according to the standard hospital practice at ICDDR,B.

Control group

The patients under control group will receive standard management which is advised to take WHO-ORS at home for maintenance of hydration and to continue his/her usual diet or as advised by hospital physician.

Follow-up:

All patients will be followed-up by home visits on every alternate day up to day 15 and then every 2 weeks thereafter up to 4 weeks. The children will be examined thoroughly including anthropometry at every follow up. Study personnel will also monitor the preparation of diet at home. Samples of prepared diet will also be collected and stored in deep freezer for quality study (e.g. composition and calories).

Fig. 1

DIETARY TREATMENT ALGORITHM

[figure not shown]

Table 1. Composition of study diets

Diet A		Diet B	
Milk/Suji/Litre (>4 mo age group)		Full-Strength Rice Suji/L	
Whole milk powder	40 g	Rice powder	60 g
Rice powder	40 g	Egg white	100 g (four)
Sugar	25 g	Oil (Soya)	30 ml
Oil (Soya)	25 g	Glucose	35 g
Mag. Chloride	0.5 g	Kcl	01 g
Potassium chloride	01 g	Mag. Chloride	0.5 g
Calcium	02 g	Calcium	02 g

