After cooked volume	1000 ml	After cooked volume	1000 ml
Energy	67kcal/100ml	Energy	70 kcal/100 ml
Protein	4.4 gm/100ml	Protein	1.88 g/100 ml
PER*	8%	PER	10%

Table 2. Composition of Multivitamin drop (Composition per 1 ml)

Vitamin A U.S.P.	5000 IU
Vitamin D B.P.	640 IU
Ascorbic Acid (C) B.P.	50 mg
Thiamine Hcl (B ₁)	1.6 mg
Riboflavin Sodium Phosphate (B ₂) B.P.	1.37 mg
Pyridoxine B.P. (B ₆) U.S.P.	1.0 mg
Nicotinamide B.P.	10.0 mg
D-Panthenol U.S.P.	5.0 mg
Folic acid	0.25 mg

Justification of selection of diet A in the beginning

Dietary treatment algorithm is a well recognised treatment schedule for the nutritional management of children suffering from persistent diarrhoea. In ICDDR hospital, this treatment algorithm is also being followed. Justification of using Diet A initially is that this diet is easy to prepare, culturally acceptable, less modified as compared to Diet B. and less expensive (1 L Diet A costs Tk. 18.00 vs. Tk. 26.00 for Diet B).

Study withdrawal

Patients will be considered withdrawn from the study if a) their parents withdraw informed consent, or b) needs hospital care.

Patients will be considered for hospital care for the following reasons:

a) appearance of signs of some dehydration b) signs of severe infections (e.g. fever, cough, respiratory distress, tachycardia, tachypnoea, reluctant to feeding etc. c) signs of electrolyte imbalance (e.g. less responsive to environments or irritability, abdominal distensions etc.). After hospitalisation, the patients will be managed according to the standard hospital practice. Patients will be followed up even after withdrawn from the study. Data obtained from the withdrawn patients will also be included in the analysis upto the time of withdrawal.

Sample size

Sample size was calculated on the basis of two major outcome variables:

- a) success rate of diet therapy
- b) Growth faltering (percentage of patients experiencing weight loss during the study periods).

Based on the study (21) the sample size of this study is determined to be of 137 in each group on anticipated success rate (combining success of Diet A and Diet B) of 80% in the intervention group against an arbitrary standard success rate of 65% in the control group, considering a significance level of 5% and power of 80%. Assuming a dropout of 15%, a total sample of 320 patients was calculated.

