We are not expecting significant difference in recovery rate on diet A and the control. However, if the difference is 20% or more, then the present sample size will be enough to detect the significant difference.

Thirty percent of children under control group is anticipated to experience weight loss as opposed to 10% in the intervention group during the study periods. Considering a significance level of 5% and 80% power, the sample size in each group is calculated as 60.

Finally, we consider the total sample size for this study as 320.

Organization of the trial

Patients attending in the treatment centre of ICDDR,B will be evaluated for recruitment for study.

Study Schedule

The study will be started after the approval of RRC and ERC and allocation of budget. The first two months will be utilized for staff recruitment, training and pretrial. 20 months will be needed for patients study. Last 2 months will be utilized for data analysis and reporting of the study results.

Definition

Diarrhoea: Three or more abnormal stools (loose or watery) during a 24-hour period.

Stool consistency: Abnormal stool - loose/watery or abnormal as considered by mother.
Normal stool - soft/formed or normal as considered by mother.

Cessation of diarrhoea: Last abnormal stool followed by normal stool at least for three days.

Success of diet therapy: Cessation of diarrhoea within 7 days of starting of the modified diet (diet A or diet B).

Facilities Available

Describe the availability of physical facilities at the place where the study will be carried out. For clinical and laboratory-based studies, indicate the provision of hospital and other types of patient's care facilities and adequate laboratory support. Point out the laboratory facilities and major equipments that will be required for the study. For field studies, describe the field area including its size, population, and means of communications. (TYPE WITHIN THE PROVIDED SPACE).

ICDDR,B treatment centre will be used for patients recruitment, observation, and training of the caregivers of the patients.

Data Analysis

Describe plans for data analysis. Indicate whether data will be analyzed by the investigators themselves or by other professionals. Specify what statistical softwares packages will be used and if the study is blinded, when the code will be opened. For clinical trials, indicate if interim data analysis will be required to monitor further progress of the study. (TYPE WITHIN THE PROVIDED SPACE).

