Statistical analysis

Statistical analysis will be done using SPSS/PC software. Percentage of success of treatment for each dietary intervention and overall success rate will be calculated. Relative risk ratios and their associated 95% confidence intervals will be calculated to identify variables (e.g. inappropriately making and feeding the diet, associated other infections, education of mothers, family income, no. of children in the family, source of drinking water, antibiotic use before admission, type of dehydration before intervention, frequency of stool etc.) that were related to the treatment failure. Overall success rate (the number of patients recovered at the end of 10 days) in the intervention group will be compared with that of control group. The number of patients lost weight will also be compared between the groups.

Adjusted analysis will be done by constructing life tables of the two groups and will be compared by log rank test.

Ethical Assurance for Protection of Human Rights

Describe in the space provided the justifications for conducting this research in human subjects. If the study needs observations on sick individuals, provide sufficient reasons for using them. Indicate how subject's rights are protected and if there is any benefit or risk to each subject of the study.

This intervention study will be conducted among the children under 5 years of age because these children are the sufferers from this illness of persistent diarrhoea. Written informed consent will be duly signed by the parents or legal guardians.

There is no risk for this intervention on the other hand they might be benefited from this intervention.

Use of Animals

Describe in the space provided the type and species of animal that will be used in the study. Justify with reasons the use of particular animal species in the experiment and the compliance of the animal ethical guidelines for conducting the proposed procedures.

Not applicable.

Literature Cited

Identify all cited references to published literature in the text by number in parentheses. List all cited references sequentially as they appear in the text. For unpublished references, provide complete information in the text and do not include them in the list of Literature Cited. There is no page limit for this section, however exercise judgment in assessing the "standard" length.

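### Need for hospital care before recovery is handled as withdrawal with data cut at that point, which is informative censoring in the planned life table and log-rank test

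*Protocol*

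**What the plan says.** Protocol, Study withdrawal: "Patients will be considered withdrawn from the study if a) their parents withdraw informed consent, or b) needs hospital care". The reasons listed for hospital care include "appearance of signs of some dehydration", signs of severe infection and signs of electrolyte imbalance. The rule covers both arms. The section goes on: "Patients will be followed up even after withdrawn from the study". It then limits what is used: "Data obtained from the withdrawn patients will also be included in the analysis upto the time of withdrawal".

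Protocol, Statistical analysis, plans two comparisons of recovery. The first is a proportion: "Overall success rate (the number of patients recovered at the end of 10 days) in the intervention group will be compared with that of control" patients. The second is called an adjusted analysis and is done by "constructing life tables of the two groups and will be compared by log rank test".

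Protocol, Definition, describes success as "Cessation of diarrhoea within 7 days of starting of the modified diet (diet A or diet B"). Hospital admission is not mentioned there, and no section says how a child admitted before cessation is classified.

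Protocol, Case management, Intervention group, adds an admission in that arm only: "After 7 days of second dietary regime, if diarrhoea persists, the patients will be admitted to the inpatient department".

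**The concern.** A log-rank test and a life table assume that children censored on a given day have the same later chance of recovery as those still observed. Here censoring is triggered by worsening illness, and one trigger, dehydration, is a direct consequence of continuing diarrhoea. The hypothesis is that these children can be managed at home, so a child who has to leave home care before recovering is evidence on the question itself. The plan removes that child from the risk set and so raises the estimated recovery of whichever arm has more such children. A true benefit could be hidden or a false one produced. The follow-up that would avoid this is already planned and then left unused.

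**Working it through.** **Inputs from the protocol (Sample size).** Success 80% vs 65%, significance level 5%, power 80%, 137 per group, 15% dropout, 320 in total, hence 160 per arm.

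**Inputs assumed, because the protocol gives none.** The shares admitted before recovery, hI (intervention) and hC (control); admission day uniform on days 1-7; recovery day uniform on days 1-14; a 14-day life-table horizon; no admitted child would otherwise have recovered by day 14.

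**Step 1: the plan's own figure.** Two-sided test of two proportions with pooled variance under the null: n = [1.96·√(2·0.725·0.275) + 0.8416·√(0.80·0.20 + 0.65·0.35)]² / 0.15² = 137.9, i.e. 138; unpooled variance gives 136. The stated 137 is reproduced. For the total, 274/0.85 = 322.4 against 320 stated. The sample size is not in dispute. With 160 per arm and every child kept, the power of this comparison is 85.5%.

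**Step 2: what censoring does to the life-table estimate.** If admitted children leave early without recovering, estimated recovery approaches p/(1−h). At 10% admitted in both arms this is 0.80/0.90 = 88.9% and 0.65/0.90 = 72.2%. The simulated life table gives 88% and 71%, a contrast of about 17 points in place of 15.

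**Step 3: what it does to the log-rank test.** Simulation, 160 per arm. The last column keeps admitted children at risk, without an event, to day 14.

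| True success | Admitted hI / hC | Quantity | Censored at admission | Kept at risk |
|---|---|---|---|---|
| 80% vs 65% | 10% / 10% | power | 88% | 79% |
| 80% vs 65% | 5% / 15% | power | 42% | 79% |
| 80% vs 65% | 5% / 20% | power | 19% | 82% |
| 65% both | 10% / 10% | type I error | 5.5% | about 5% |
| 65% both | 15% / 5% | type I error | 21% | 5% |

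Repeat runs gave 40% to 42% for the second row and 20% to 22% for the last. When there is no true difference, the false positives almost all favour the arm with more admissions.

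**Step 4: sensitivity to the assumptions.** A smaller imbalance matters less: at 5%/8% power is 76% and type I error 5.7%; at 5%/10% power is 66%. If half of the admitted children would have recovered, power at 5%/15% is 71%, and type I error at 15%/5% is 5.9%.

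**Step 5: the success rate.** If withdrawn children stay in the denominator as not recovered, 80% vs 65% is unchanged. If they are dropped, 5%/15% gives 0.80/0.95 = 84.2% vs 0.65/0.85 = 76.5%, a difference of 7.7 points with power 38%.

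**Step 6: admission after Diet B.** Seven days of Diet A and seven of Diet B place it at about day 14. That is after the 10-day reading of success and at the end of the horizon used here, so it cannot censor either. Home visits run to 4 weeks (Follow-up), so weights after about day 14 could be lost in the intervention arm only, if this admission counts as a withdrawal.

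**The case against.** **The success rate is not shown to be biased.** A reader might infer that it is. The Statistical analysis section counts those recovered at 10 days and gives no denominator; a child withdrawn unrecovered is simply not in that count. The withdrawal sentence speaks of including these children's data, not of dropping the children. This stands: bias in the proportion is conditional.

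**The log-rank test is not the comparison the trial is sized on.** Sample size rests on two binary outcomes, success and weight loss, and the log-rank test is labelled an adjusted analysis. This stands: 42% is not the power of the sized comparison. The log-rank test is nevertheless a stated between-arm test of recovery.

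**The arms are not treated unequally for recovery.** A reader might infer that the Diet B admission tilts the recovery comparison. Its timing rules that out, and the withdrawal rule itself is common to both arms. What remains is a possible one-sided loss of later weights, which has not been quantified.

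**The magnitudes depend on the scenario.** Equal shares keep type I error near 5%, and Step 4 shows the effect shrinking under milder assumptions. This stands for size and direction. It does not make the censoring uninformative.

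**Not every admission is a diet failure.** Severe infection is a trigger, and success is defined by cessation of diarrhoea alone. This is fair, and it is the reason for the sensitivity analysis below. Such a child has still not recovered at home by that time.

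**Post-admission data may be mixed.** The protocol says that its hospital also follows this dietary algorithm, so weights after admission in controls could partly reflect the intervention diet. That is a caution for interpretation and does not justify discarding the data in either arm.

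**Conclusion.** The defect holds, and it is a rule the protocol states outright, not a detail left open. Following it makes the life table and log-rank test censor children because they worsened. Recovery is overstated in any arm with such admissions, and the test is distorted when shares differ. With equal shares type I error is held, but the contrast is exaggerated.

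The illustrative sizes (power about 42% instead of 79%; type I error about 21% instead of 5%) rest on a threefold imbalance in admissions and on no admitted child otherwise recovering. The protocol supports neither assumption nor its opposite. The documents do not show which arm would be favoured, that the success rate is biased, or that the Diet B admission affects recovery at 10 days.

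**What to change.** Replace the last sentence of Study withdrawal so that:

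- all randomised children are analysed in their allocated arm and form the denominator of the success rate;
- a child who needs hospital care before cessation of diarrhoea counts as not recovered and, in the life table, stays at risk without an event to the end of a stated horizon;
- only withdrawal of consent or loss to follow-up is censored;
- weights from the continued follow-up are used in both arms;
- a sensitivity analysis uses the recovery actually observed after admission.

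The Case management and Study withdrawal sections should also be reconciled on whether admission after Diet B is a withdrawal. No rule for admission or referral is proposed.

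The cost is wording only, since follow-up after withdrawal is already planned. The downside is that success rates will be somewhat lower, and a child admitted for an infection unrelated to the diet will count as not recovered at home.

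### Children admitted to hospital are still followed up but analysed only to admission, which truncates their weight outcome and makes life-table censoring informative

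*Protocol*

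**What the plan says.** The rule is in the protocol section Study withdrawal, which combines two different events: "Patients will be considered withdrawn from the study if a) their parents withdraw informed consent, or b) needs hospital care". The clinical reasons for hospital care listed there are signs of some dehydration, of severe infection and of electrolyte imbalance. Two further statements in the same section set out what follows:

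- Observation of these children continues: "Patients will be followed up even after withdrawn from the study".
- What enters the analysis is nevertheless cut short: "Data obtained from the withdrawn patients will also be included in the analysis upto the time of withdrawal".

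The comparisons affected are described elsewhere in the protocol:

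- **Weight loss.** This is one of the two outcomes used for sample size: "Growth faltering (percentage of patients experiencing weight loss during the study periods". The Follow-up section plans weighing throughout: "The children will be examined thoroughly including anthropometry at every follow up".
- **Life tables.** The Statistical analysis section plans life tables for the two groups, compared by log rank test, as the adjusted analysis. It does not name the event. Time to cessation of diarrhoea is the natural reading.
- **Success.** The same section compares the number recovered at 10 days between the groups.

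**The concern.** An SAP could fill a gap, but this is a rule that the protocol itself fixes, and an analysis plan that followed it would inherit the problem. The data are cut because the child has deteriorated, although the trial still intends to collect what comes afterwards.

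For weight loss, weight lost after admission goes unseen. Alternatively, a weight taken while the child is dehydrated becomes the last one on record. The error can therefore go either way.

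For the life table, using data only to withdrawal means censoring at admission. The log rank test then treats an admitted child as if the chance of recovering at home were the same as for children still at risk, when the child was removed for doing badly.

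The hypothesis is that these children can be managed at home. A need for hospital care before the diarrhoea stops is evidence on that question and should not be handled as missing data.

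**Working it through.** **Inputs from the protocol.** Success 80% against 65%, 137 per group; weight loss 10% against 30%, 60 per group; 5% significance, 80% power; 15% dropout; 320 in total, so 160 per arm.

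**The plan's own figures.** With the pooled two-sided formula, n = [1.96·√(2·0.725·0.275) + 0.8416·√(0.80·0.20 + 0.65·0.35)]² / 0.15² = 138 per group (stated 137; the unpooled formula gives 136). Then 137/0.85 rounds up to 162 per group, 324 in total (stated 320). For weight loss the pooled formula gives 62 (stated 60; unpooled 59). The sample size reproduces, so the point does not rest on an arithmetic error.

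**Assumptions, because the protocol gives no admission rates.** Admission is taken as 5% to 15% per arm. The upper end borrows the dropout allowance ("Assuming a dropout of 15%, a total sample of 320 patients was calculated"; 0.15 × 320 = 48 children), which does not separate admission from other losses. Admitted children are assumed not to recover within the analysis window.

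**Weight observation lost.** The scheduled visits fall on days 3, 5, 7, 9, 11, 13, 15 and about 29, which is 8 follow-up weighings. A child admitted on day 5 keeps 2 of them.

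**Weight loss.** The planning statement is: "Thirty percent of children under control group is anticipated to experience weight loss as opposed to 10% in the intervention group". With 160 per arm that is 48 against 16 children, (48 − 16)/160 = 20.0 points (Newcombe 95% CI 11.4 to 28.4). Suppose half of the admitted children lose weight only after admission:

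| Admitted, intervention / control | Losses missed, intervention / control | Observed, control vs intervention | Difference (95% CI) |
|---|---|---|---|
| 5% / 15% (8 / 24) | 4 / 12 | 36 vs 12 | 15.0 (7.3 to 22.7) |
| 15% / 5% (24 / 8) | 12 / 4 | 44 vs 4 | 25.0 (17.6 to 32.5) |
| 15% / 15% (24 / 24) | 12 / 12 | 36 vs 4 | 20.0 (13.1 to 27.2) |

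With equal admission the difference is unchanged, but both rates are too low.

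**Life table, limiting case.** If every admission came before any recovery, censoring would be the same as removal, and the estimated recovery would be p/(1 − w), where p is the true recovery rate and w the proportion admitted. With a true 65% in both arms and 15% against 5% admitted: 0.65/0.85 = 76.5% and 0.65/0.95 = 68.4%, a spurious gap of 8.0 points in favour of the arm with more admissions. Later admission gives a smaller gap.

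**Log rank test by simulation.** 160 per arm; recovery follows an exponential curve to the stated 10-day rate; admission on day 3, 5 or 7 with equal chance.

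| True recovery, intervention / control | Admitted, intervention / control | Rejects, censored at admission | Rejects, kept at risk |
|---|---|---|---|
| 65% / 65% | 15% / 5% | 10% to 13% | about 5% |
| 65% / 65% | 10% / 5% | 6% to 7% | about 5% |
| 65% / 65% | 10% / 10% | 5% to 6% | about 5% |
| 80% / 65% | 5% / 15% | 77% | 90% |

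The ranges cover repeated runs with a Monte Carlo error of about 1 to 2 points. Timing matters. In the 15% / 5% null case, spreading admission over days 1 to 7 and recovery evenly to day 14 gives about 23%, and moving all admissions to day 1 gives 26% to 33%.

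**The case against.** Several counter-arguments have force.

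**Success rate.** A reader might infer that admitted children drop out of the 10-day success denominator. Under the 5% / 15% and 15% / 5% assumptions that would turn the planned 15 points into 7.7 or 25.7. No statement in the protocol supports this. Withdrawn children's data are to be included, and a child admitted with continuing diarrhoea has data showing no recovery, so the natural result is not recovered and still counted. On that reading the comparison stays at 80% against 65%, and the two figures are purely hypothetical.

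**Life table.** The protocol names neither the event nor a censoring rule, and the harm is modest unless admissions are very unequal or very early. This stands, and it is why the claim is conditional.

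**On-home-treatment analysis.** It can be argued that stopping at admission suits a home-care question. This does not hold, because admission before cessation is itself evidence against treatability at home.

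**Contamination.** The justification for diet A says that the hospital also follows the dietary algorithm, so admitted control children may receive it. Weights after admission then partly mix the arms. This stands and has to be handled in the fix. Children admitted for dehydration or poor feeding may also have lost weight already, which would make the weight examples too large.

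**Other inferences.** A reader might conclude that deaths after admission go uncounted. Mortality is not a planned comparison, and continued follow-up would allow deaths to be recorded. Nor is it stated that admission for failure of diet B ("if diarrhoea persists, the patients will be admitted to the inpatient department") counts as withdrawal. It comes after day 10 in any case.

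**Conclusion.** The point holds for weight loss and, if the event is cessation of diarrhoea, for the life table. The protocol fixes an outcome-related cut-off and discards follow-up that it already plans to collect. It does not support a claim that the trial is biased in a particular direction or by a known amount, because admission rates are not given.

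Under the assumptions shown, a threefold imbalance in admission (15% against 5%) on days 3 to 7 raises the false-positive rate of the log rank test from about 5% to roughly 10% to 13%, and further if admission is earlier. The planned 20-point weight difference would be observed as 15 or 25 points if half of the admitted children lost weight only afterwards. With equal admission rates the test stays near its nominal level. The sponsor should change the rule, but the point does not invalidate the design.

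**What to change.** Replace the last sentence of Study withdrawal with:

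> Data are used up to withdrawal only when parents withdraw consent to further data. All other randomised children, including those admitted, are analysed in their randomised group to the end of planned follow-up. Admission for the listed reasons, or death, before cessation of diarrhoea counts as not recovered in the 10-day success rate, and the child stays at risk as not recovered in the life table rather than being censored at admission. Weights after admission are included in the weight-loss comparison.

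In Statistical analysis, add a sensitivity analysis of weight loss using weights up to admission only, because admitted control children may receive the same algorithm in hospital. Report admissions and deaths by group.

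**Cost.** A few sentences, one descriptive table and one sensitivity analysis. There are no new visits or staff, since withdrawn children are already followed up.

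**Downsides.** Weight after admission partly reflects hospital treatment, including possible exposure of controls to the algorithm. The unblinded decision to admit becomes part of the success endpoint. Some admissions for infection will have nothing to do with diet.
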